Participants can complete the intervention by telephone and/or during off hours (evenings, weekends) to facilitate participation. If we find participants are too severely impaired to benefit (see exclusion criteria), we will link them to mental health or substance abuse services and resources via the care manager.

We will offer a 'flexible approach' option. If someone is eligible after the screener but reports not being interested in participating in the study, we will ask permission to contact them 3 more times within a 6 month period (2 months after the first screening interview, 4 months and 6 months after). If they agree, we would contact them every 2 months to rescreen them and try to enroll them into the trial. 6 months after the first screening interview (after 3 calls), if the person still reports not being interested in participating, we will assume the case to be a decline to enroll, and not contact him/her again. If, after the first screening interview the person who is not interested in being enrolled asks the RA not to continue to contact them, we will also mark the case as declining to enroll.

Participants in the enhanced usual care group will receive an NIH booklet about anxiety and depression in Spanish, English, or Mandarin/Cantonese. The Care Manager will call the participant 4 times over the course of 6 months to administer the PROMIS, the 5-item suicide questionnaire, and a question about medication side effects to mimic the administration schedule in the intervention group, with data entered in Dimagi CommCare. With the participant's permission, the care manager will inform the PCP about screening and other assessments and determine if participants should be referred to mental health or substance services and removed from control group given severity (PHQ-9 ≥ 20 , GAD-7 ≥ 15 and Paykel

=4 or 5 or active substance use). This will be considered a positive outcome for participant safety.

All enrolled participants (intervention and usual care) will be contacted for assessments over the course of 12 months: baseline, and 3-month, 6-month, and 12-month follow-ups.

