The target sample size was designed to achieve adequate power for our research questions. Using data from prior studies on the effectiveness of similar interventions, the estimated effect size for the outcomes ranged from 0·24 to 0·68. The nonparticipation rate of enrolled participants was assumed to be 13%. Our sample size of 1,200 (600 treatment and 600 control) from North Carolina and Massachusetts is thus effectively 1044. This sample yielded 87% power to detect an intervention effect size of 0·20, with a two-sided significance level of 0·05. Testing whether there is a differential effect of Strong Minds-Strong Communities based on participants' race and ethnicity means trying to determine whether race and ethnicity moderated the impact of the intervention. The racial and ethnic composition of our sample was roughly 63% Latinx, 14% non-Latinx Black, 13% Asian, 9% White, and 1% other races or ethnicities. Assuming a large effect size of the intervention for White participants ($> 0\cdot5$), a small effect size for Black participants ($< 0\cdot3$), and a medium effect size for Asian and Latinx participants ($> 0\cdot3$ and $< 0\cdot5$), we will have 80% power to detect a significant intervention effect in each racial and ethnic group with a sample size of 1044. Similarly, testing whether there is a differential effect of Strong Minds-Strong Communities in North Carolina compared to Massachusetts means testing whether site moderated the impact of the intervention.

VIII. Risks and Discomforts

A. Psychosocial (non-medical) risks:

The safety of intervention participants will be closely monitored during the Strong Minds-Strong Communities intervention. Participants will be administered the PHQ-9 depression screener and the GAD-7 anxiety screener during research interviews and biweekly during intervention sessions, and in biweekly check-ins for usual care participants. If participants endorse the Item

9 suicidality question of the PHQ-9, they will be administered the Paykel Suicidality Screener.

Those who endorse questions 4 and 5 of the Paykel, suggesting active suicidality, will be provided emergency care following emergency protocol developed by the research team.

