In the event that a participant endorses Items 4 and 5 of the Paykel Suicidality Screener (see above), the CHW or CRC administering the assessment will follow the Emergency Protocol. The protocol calls for an assessment by the local emergency services. The research team member will follow up with the participant within 24 hours. If the person is admitted to emergency psychiatric services, the research team member will follow up with the participant after 30 days. If the participant no longer reports suicidality, he/she will be allowed to continue to the study. In no case will a participant with elevated symptoms be removed from the study without ensuring an appropriate referral. If a participant scores in the severe range on the PHQ-9 or the GAD-7 (corresponding to scores of greater or equal to 20 on the PHQ-9 or greater or equal to 15 on the GAD-7) for two or more assessments, that participant will be monitored closely and the CHW's supervisor will determine whether that individual should be referred to specialty treatment. Depending on the nature of the treatment, the participant may be allowed to continue with the study. The following criteria will be used to remove a subject from the study. The participant's primary care provider will be notified if his/her symptom assessment scores remain in the severe range.

IX. Potential Benefits

A. Potential benefits to participating individuals

In terms of efficacy, it is hoped that this intervention will contribute to reduced depression and/or anxiety among a significant proportion of study participants. Depressive and anxiety symptoms from baseline will be measured by the Hopkins Symptom Checklist-25, the PHQ-9, and the GAD-7, and disability days as measured by the WHO-DAS 2.

B. Potential benefits to society (e.g. increased understanding of disease process, etc.)

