The emergency procedure is prompted if a patient endorses a 4 or 5 on the Paykel suicidality screener over the last 30 days. The questions include: “Has there been a time in the last 30 days/since the last assessment when you reached the point where you seriously considered taking your own life, or perhaps made plans how you should go about doing it?” = yes or “Has there been a time in the past 30 days/since the last interview when you made an attempt on your own life?” = yes.

- 1) At the end of the session or interview, study staff should inform the participant: *“I am not a clinician; however, when anyone tells us they’ve been feeling this way recently, we connect them with a clinician who can ask some questions about how you’ve been feeling. We will also contact your primary care doctor to let them know about this conversation and make sure you are safe. We want to ensure your safety, so let me connect you right now. Could you please tell me where you are located right now?”*

2) **Study staff should immediately connect the patient to the correct Emergency Services provider** for assessment.

- Place the patient on hold (or have them wait a moment when in person).
- When speaking to emergency services team, refer to the study: I have a patient on the line as part of the research study who scored high on a suicide screening tool. I am not a clinician, and am hoping the patient can be assessed for risk by phone -- he/she has given consent to this as part of the study.
- Take the name of the person who you are talking to.
- The emergency services provider will need the following information from you:
 - patient's name
 - phone number
 - present location
 - what was said by patient re: suicidality
- If a Spanish, Mandarin, or Cantonese speaking clinician is not readily available, study staff are allowed to translate only in the capacity of informing the patient of what the emergency services provider says are the 'next steps' (i.e., someone is going to call you back in 5 minutes, etc.)

If for some reason, the participant is not able to be or refuses to be connected right away you should:

- 1) Provide the patient with the emergency services contact number, depending on where they are located.

2) Contact the emergency services provider based on where the patient is located and share the pertinent information as described above. Immediately inform the study PI and your supervisor.

Emergency Protocol Documentation Form

Patient ID #: _____

Date: _____

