Items endorsed:

4 on the past 30 days Paykel

5 on the past 30 days Paykel

Description of event: _____

Primary Care Provider's name: _____

Information to collect for Emergency Services

Name _____

Contact phone number right now _____

Where the patient is right now _____

What the patient said about suicidality _____

Patient Date of Birth (if available) _____

Patient Insurance (if available) _____

Name of person who you talked to _____

Post-call checklist

Send Message to PCP _____

Email to Site Leader and PI _____

Inform PCP of outcome _____

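### Section VIII.A sets the suicide-emergency trigger at Paykel items 4 and 5, the emergency protocol it relies on sets it at 4 or 5; VIII.A should say *or*

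*Combined protocol and SAP*

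**What the plan says.** Section VIII.A (Psychosocial (non-medical) risks) states the trigger twice. Its first paragraph says: "Those who endorse questions 4 and 5 of the Paykel, suggesting active suicidality, will be provided emergency care". A later paragraph of the same section begins: "In the event that a participant endorses Items 4 and 5 of the Paykel Suicidality Screener (see above". Each sentence then refers staff to the emergency protocol. The later paragraph adds what happens next: "The research team member will follow up with the participant within 24 hours", and "If the person is admitted to emergency psychiatric services, the research team member will follow up with the participant after 30 days".

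Section XI.A (Sample Self-Harm/Risk Emergency Protocol) states the trigger differently: "The emergency procedure is prompted if a patient endorses a 4 or 5 on the Paykel suicidality screener over the last 30 days". It prints both questions and joins them with *or*. The first asks whether the person "seriously considered taking your own life, or perhaps made plans how you should go about doing it"; the second asks about an attempt.

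The Emergency Protocol Documentation Form gives each item its own line, for example "4 on the past 30 days Paykel". Section VI has a referral and removal rule for the enhanced usual care group, which is not the emergency trigger; its Paykel part also uses *or*: "4 or 5 or active substance use".

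**The concern.** The trigger decides whether a participant who discloses suicidality is sent for emergency assessment. It is applied by community health workers and research coordinators, whose script has them tell the participant that they are not clinicians. Such staff need one unambiguous rule.

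Read literally, VIII.A requires both items. It would then not escalate a participant with a current plan and no attempt, or one who reports an attempt but does not endorse item 4. Either is an emergency under XI.A.

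XI.A repairs the first step, connection to emergency services, but not the later ones. The timed follow-up contacts appear only in the VIII.A paragraph that opens with the *and* condition.

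**Working it through.** The plan gives no figure to reproduce. The check compares the texts and counts response patterns.

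**Where each version appears**

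| Place | Rule | Function |
|---|---|---|
| VIII.A, first paragraph | 4 *and* 5 | emergency care |
| VIII.A, later paragraph | 4 *and* 5 | emergency assessment and follow-up |
| XI.A | 4 *or* 5 | starts the emergency procedure |
| Documentation form | separate lines for 4 and 5 | record of items endorsed |
| Section VI | 4 *or* 5 | usual-care referral and removal, combined with other scores |

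That is two statements with *and* and two with *or*, plus a form that allows one item to be recorded alone.

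**Response patterns (item 4, item 5)**

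| Pattern | VIII.A read literally | XI.A |
|---|---|---|
| no, no | no | no |
| yes, no | no | yes |
| no, yes | no | yes |
| yes, yes | yes | yes |

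*Or* triggers in 3 of 4 patterns and *and* in 1 of 4. The texts differ in 3 − 1 = 2 patterns: item 4 alone and item 5 alone.

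**Follow-up steps**

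- VIII.A, later paragraph: 2 timed contacts with the participant (within 24 hours; after 30 days if admitted). The same paragraph holds the rule on continuing in the study once suicidality is no longer reported.
- XI.A and its form: 0 later contacts by study staff with the participant. The three post-call entries are a message to the primary care provider, an email to the site leader and PI, and a report of the outcome to the primary care provider.

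So, of the 3 patterns that start XI.A, the two follow-up contacts are literally written for 1 (both items endorsed). With *or* in VIII.A they are written for all 3.

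These are counts of patterns, not rates. The documents do not say how often either item is endorsed, so no count of participants follows from them.

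**The case against.** The best defence is that the text staff actually work from is already right. VIII.A is a risk summary that defers to the emergency protocol. That protocol prints both questions with *or* between them, and the form treats the items separately. *Questions 4 and 5* can also be read as naming the two items that signal active suicidality, without requiring both. The follow-up sentences in VIII.A can likewise be read as what happens once the protocol is activated, and XI.A activates it on either item. On that reading nobody loses follow-up. Other safeguards do not depend on the wording: weekly clinical supervision, close monitoring of participants at risk, biweekly symptom checks in both arms, and a registry reviewed weekly.

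Much of this stands. *Or* is clearly the intent, staff using XI.A should make the emergency connection correctly, and the follow-up gap exists only on a literal reading. Three things limit the defence:

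- The lead-in to XI.A calls it an example for intervention participants, to be adapted to each site. It cannot be relied on to override VIII.A, which carries no such label and whose monitoring text also covers usual-care participants.
- The loose reading of *and* fits the later paragraph less well, since that sentence concerns a single participant endorsing the items.
- None of the other safeguards sets a contact within 24 hours or after an admission.

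The Section VI rule is only weak support, because it serves a different purpose.

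**Conclusion.** The inconsistency is real and should be fixed. The plan states a safety threshold two ways, and the sections disagree for 2 of the 4 response patterns. On a literal reading, the 24-hour and post-admission contacts are written for only 1 of the 3 patterns that start the emergency protocol.

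The mismatch in wording is certain. The follow-up gap rests on taking the VIII.A paragraph literally, so that its first sentence governs those that follow. Nothing in the documents shows that any staff member applied *and* or that any participant went without follow-up. The point does not bear on endpoints, power or analysis.

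**What to change.** Make two edits in Section VIII.A:

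1. First paragraph: replace *questions 4 and 5* with *question 4 or question 5*.
2. Later paragraph: replace *Items 4 and 5* with *Item 4 or Item 5*, and leave the rest as it stands. The emergency assessment, the 24-hour contact and the 30-day contact after admission then apply when either item is endorsed.

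Section VI, Section XI.A and the documentation form need no change.

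The cost is two wording edits. Because XI.A already requires activation on either item, the edits should add few if any emergency calls. The main added work is the 24-hour contact, and the 30-day contact after an admission, for participants who endorse only one item.
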